Interestingly, an intrinsically angiogenic impairment is also described in pregnancies complicated by congenital heart disease (CHD). (6) In particular, PIGF levels are found to be significantly lower and sFlt-1 levels significantly higher in the maternal plasma from pregnancies with fetuses with CHD in comparison to controls; so, women with pregnancies complicated by CHD show a similar circulation profile of women developing PE (6). This has been the scientific rationale for investigating the relationship between CHD and maternal increased risk of PE.–A Norwegian register-based study recently found associations between PE and CHD: in particular, early-PE is strongly associated with infant risk of CHD (7). Simultaneously, a Canadian population-based study found that overall PE was significantly associated with noncritical heart defects in offspring, whereas early-PE was associated with critical heart defects (8). Boyd H et al. in their study including 18,000 fetuses with CHD and 55,000 pregnancies with preeclampsia, have demonstrated that women carrying a fetus

with CHD, regardless of the type of defect, had a 7-fold increase in the risk of early-PE and 3-fold increase in the risk of late-preterm PE, whereas the association with term PE was weakly (9). Interestingly, women who had a previous child with CHD had a 2-fold greater risk of early PE and a 25% greater risk of term PE. Conversely early PE in a previously pregnancy was associated with a 6-fold increased risk of offspring CHD in the current pregnancy (10; 9). Moreover, placental histopathology examinations from pregnancies who underwent termination of pregnancy because of severe CHD showed that placental vascular malperfusion lesions were more common as compared with other fetal malformations (11).

However, new interesting theories regarding the pathogenesis of PE have been recently highlighted: in particular, there is now emerging evidence that a suboptimal maternal cardiovascular performance resulting in uteroplacental hypoperfusion is more likely to be the first cause of placental dysfunction in preeclampsia. (12; 13) There are now several data from maternal echocardiography and angiogenic marker studies showing that cardiovascular dysfunction precedes the development of preeclampsia by several weeks or months (10). It is now well known that the cardiovascular system is markedly compromised in PE and plays a major role in the development of PE complications. Recent studies have elucidated the maternal hemodynamic profile associated with early-PE showing how this is typically associated to high maternal systemic vascular resistance (SVR) and low cardiac output (CO) (13). The recognition of the role of the cardiovascular etiology in PE has deep implications not only for the definition the pathophysiology of the disease but also for PE screening and diagnosis, clinical management, and therapy as recently the maternal hemodynamic assessment has entered in the clinical practice.

Although the similar pathogenic profile associated with PE and CHD and the well demonstrated data about the risk of PE in pregnancies complicated with CHD, to our knowledge, no investigations about maternal hemodynamic profile in these pregnancies has been previously proposed.

The aim of this study is to explore the maternal hemodynamic parameters detected by UltraSonic Cardiac Output Monitor (USCOM®) in women carrying a fetus with CHD and to eventually describe an association between those parameters and the presence of a fetal cardiac anomaly.

OBJECTIVES

Primary Objective: The aim of this study is to describe the maternal hemodynamic parameters detected by UltraSonic Cardiac Output Monitor (USCOM®) in women carrying a fetus with CHD and to possibly describe an association between those parameters and the presence of a fetal cardiac anomaly.

Secondary Objectives:

- To assess the number of cases of PE in our population of women carrying fetuses with CHD
- To assess the relationship between maternal hemodynamic profile and maternal and perinatal outcome
- To investigate associations between maternal hemodynamic parameters and the specific heart defect subtype
- To explore the relationship between maternal hemodynamic parameters and fetal cardiac function and morphology in our population

METHODS

Study design This is a prospective monocentric interventional study with the use of the medical device UltraSonic Cardiac Output Monitor (USCOM®).

Study Population: Singleton pregnancy with a diagnosis of CHD performed at the Fetal Medicine Unit of Fondazione Policlinico A. Gemelli IRCCS during the study period and delivered at Fondazione Policlinico A. Gemelli IRCCS.

Study duration

The study has an expected duration of 36 months (three years). The study will begin when the ethics committee has issued a favorable opinion.

Inclusion criteria

The inclusion criteria are:

- Informed consent accepted
- Maternal Age >18 years
- Singleton pregnancy with a viable fetus at >20 weeks of gestation, with a diagnosis of CHD detected on antenatal ultrasound assessment and postnatally confirmed.

Exclusion criteria

The exclusion criteria are:

- Multiple pregnancy
- Pregnancy complicated by aneuploidy, genetic syndrome, or major structural fetal abnormality.
- Maternal congenital heart disease (GUCH)
- Maternal known cardiac disease

Variables and procedures

The following maternal hemodynamic indices will be evaluated: heart rate (HR) (beats per min; bpm), mean arterial pressure (mmHg), stroke volume (mL), cardiac output (CO) (L/min), systemic vascular resistance (dynes/s/cm⁵). Data on the demographic and pregnancy characteristics of participants, hemodynamic and ultrasound investigations, perinatal and delivery features will be also collected. In particular, the following variables will be included in the study: type of congenital heart defect, gestational age at diagnosis, fetal weight (EFW) and fetal weight centile at diagnosis of CHD and at the last scan before delivery, mean uterine arteries pulsatility index (UtA-PI), fetal umbilical artery (UA-PI) and middle cerebral artery pulsatility index (MCA-PI) at diagnosis and at the last scan before delivery, maternal age, height, pre-pregnancy weight and gestational weight gain, systolic and diastolic blood pressure values (maximum and minimum values), presence of proteinuria, biochemical maternal assessment (maximum and minimum values of creatinine and uric acid level, platelet count, liver enzyme level), incidence of hypertensive disorders of pregnancy, antihypertensive drug administration (type and dosage) including magnesium sulfate, antenatal steroid administration, mode of delivery and indications, gestational age at delivery, birthweight and birthweight centile, need of respiratory or cardiac support, neonatal intensive care unit admission and number of days, major neonatal complications, maternal morbidities (HELLP, eclampsia, intravascular disseminate coagulation, post-partum hemorrhage), and mortality. The following definitions of hypertensive disorders will be used, according to the International Society for the Study of Hypertension in Pregnancy (ISSHP) 2018 criteria (14): chronic hypertension (CH) will be defined as hypertension ($\geq 140/90$ mmHg) that predates pregnancy or is present prior to 20 weeks' gestation; gestational hypertension was defined as de-novo hypertension ($\geq 140/90$ mmHg) after 20 weeks' gestation; and preeclampsia (PE) will be defined as de-novo hypertension ($\geq 140/90$ mmHg) after 20 weeks' gestation with coexisting proteinuria, other maternal organ dysfunction or fetal growth restriction; preeclampsia superimposed to chronic hypertension (PE-CH).

Maternal hemodynamics assessment: Hemodynamic indices will be obtained using the USCOM® system. Women will undergo a hemodynamic investigation at the time of first diagnosis of CHD

during pregnancy or at the first assessment in Fondazione Policlinico A. Gemelli during pregnancy and then every two weeks until delivery. An additional hemodynamics evaluation will be performed in the post-partum period (in the 72 hours immediately after delivery). All hemodynamic assessment will be performed under standardized conditions. Maternal height, weight and brachial blood pressure will be obtained prior to hemodynamic assessment. USCOM® system utilizes continuous-wave Doppler, with a non-imaging probe in the suprasternal notch, to obtain velocity-time integrals of transaortic blood flow at the left ventricular outflow tract. Using an internal anthropometric algorithm, which correlates the outflow tract diameter with the patient's height, USCOM-1A multiplies the velocity-time integral by the aortic root diameter to calculate stroke volume. By measuring the time interval between each Doppler profile, heart rate (HR) can be calculated. CO (stroke volume \times HR) and SVR (MAP/CO) are calculated after inclusion of maternal mean arterial pressure. Participants remain in a semi recumbent position and a small amount of conducting gel is applied to their skin at the level of the suprasternal notch. The Doppler probe is applied and moved through three dimensions to ensure that the velocity of blood was being measured at the left ventricular outflow tract and not in the more distal aorta. Each Doppler acquisition used for analysis must register a minimum of two consecutive Doppler profiles (cardiac cycles). All hemodynamic measurements were performed by trained operators. USCOM-1A has been in clinical use since 2015. Its repeatability and reproducibility have been assessed in adult, pediatric and pregnant populations, demonstrating excellent agreement between operators with sufficient training (15; 16).

ENDPOINTS

Primary endpoint: To identify the maternal hemodynamic parametrics changes in pregnancies complicated by congenital heart diseases and immediately after delivery.

Secondary endpoints:

- prevalence of cases of preeclampsia in our population of pregnancies complicated by congenital heart disease
- To investigate association between maternal hemodynamic profile and perinatal outcome
- To calculate correlation coefficients between the maternal hemodynamic parameters to the specific heart defect type
- To calculate correlation coefficients between the maternal hemodynamic parameters and fetal cardiac function and morphology parameters

STATISTICAL ANALYSIS PLAN

Sample size calculation

108 patients will be recruited

Statistical analysis

The sample will be described in its clinical and demographic characteristics by descriptive statistics techniques. In depth, qualitative data will be expressed as absolute and relative percentage frequency, whilst quantitative variables either by mean and standard deviation (SD) or median and interquartile range (IQR), as appropriate.

To verify the Gaussian distribution of quantitative variables, the Shapiro-Wilk test will be applied.

The discrete variables will be compared by Chi Square or Fisher Exact test.

Correlation analysis between hemodynamic parameters and variables related to the type of congenital heart defect of the fetus will be carried out by calculating and testing Pearson's and/or Spearman's correlation coefficient, when necessary Kendall's correlation coefficient will be used. Likewise, correlation analysis between hemodynamic parameters and fetal cardiac function parameters will be carried out.

To identify any differences in mean between baseline and immediate postpartum, continuous variables will be compared with the T test for paired data and/or the Wilcoxon test when appropriate.

Regression analysis will be performed to explore the relationship between maternal hemodynamic parameters and maternal and perinatal outcome and fetal cardiac parameters.

Mixed-effects models for longitudinal data will be fit to identify potential changes over time in maternal hemodynamic parameters also in relation to fetal cardiac parameters, controlling for any confounding variables.

All results will be considered statistically significant when $p < 0.05$.

All analyses will be conducted with R statistical software (R, cran, 2023).

Safety/Adverse Event Management

All adverse events observed during the study will be collected and recorded.

Adverse events involving medical devices can be classified as incidents and deficiency, the aforementioned, as identified by the following definitions, will be reported to the National Competent Authority and to the Manufacturer according to the provisions of current legislation for medical devices (EU Regulation 745/ 2017 and Legislative Decree 5 August 2022, n.137 and subsequent communications from the Ministry of Health).

In the case of a medical device, it means for

- any untoward medical occurrence, unintended disease or injury or any untoward clinical signs, including an abnormal laboratory finding, in subjects, users or other persons, in the context of a clinical investigation, whether or not related to the investigational device.;
- any inadequacy in the identity, quality, durability, reliability, safety or performance of an investigational device, including malfunction, use errors or inadequacy in information supplied by the manufacturer;
- any incident, malfunction or alteration of the characteristics or performance of a device made available on the market, including the error of use caused by the ergonomic characteristics, as well as any inadequacy in the information provided by the manufacturer and any unwanted side effects.

A serious incident is defined as any incident which, directly or indirectly, has caused, may have caused or may cause one of the following consequences:

- a) death of the patient, user or other person
- b) serious deterioration, temporary or permanent impairment of the state of health of the patient, the user or another person;
- c) a serious threat to public health

References

1. Global and regional estimates of preeclampsia and eclampsia: a systematic review. . Abalos E, Cuesta C, Grosso AL, Chou D, Say L. 1, s.l. : Eur J Obstet Gynecol Reprod Biol. , 2013, Vol. Sep; 170.
2. Rheological and physiological consequences of conversion of the maternal spiral arteries for uteroplacental blood flow during human pregnancy. . Burton GJ, Woods AW, Jauniaux E, Kingdom JC. 6, s.l. : Placenta, 2009, Vol. Jun; 30.
3. Circulating angiogenic factors and the risk of preeclampsia. Levine RJ, Maynard SE, Qian C, Lim KH, England LJ, Yu KF, Schisterman EF, Thadhani R, Sachs BP, Epstein FH, Sibai BM, Sukhatme VP, Karumanchi SA. s.l. : N Engl J Med. , 2004, Vols. Feb 12;350(7):672-83.

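### The primary objective includes an association with the presence of fetal CHD, but only CHD pregnancies are eligible, so that clause cannot be estimated

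*Protocol*

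**What the plan says.** The association appears twice in the Protocol. The aim, in the paragraph just before OBJECTIVES, is to explore maternal haemodynamics in CHD pregnancies and "to eventually describe an association between those parameters and the presence of a fetal cardiac anomaly". The Primary Objective repeats it with a different hedge: "to possibly describe an association between those parameters and the presence of a fetal cardiac anomaly".

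Under METHODS, the Study Population is "Singleton pregnancy with a diagnosis of CHD performed at the Fetal Medicine Unit", and the inclusion criterion is "Singleton pregnancy with a viable fetus at >20 weeks of gestation, with a diagnosis of CHD detected on antenatal ultrasound assessment and postnatally confirmed". The design is given as one prospective single-centre cohort with no second group.

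Under ENDPOINTS, the primary endpoint is "To identify the maternal hemodynamic parametrics changes in pregnancies complicated by congenital heart diseases and immediately after delivery". Under STATISTICAL ANALYSIS PLAN, the sample size entry is "108 patients will be recruited". The planned analyses are:

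- a paired comparison of baseline with immediate postpartum
- correlations with defect type and with fetal cardiac function
- regression on maternal and perinatal outcomes
- mixed-effects models over time

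**The concern.** To estimate an association with the presence of a condition, some observations must come from people without it, either in the study or in a stated outside source. The protocol supplies neither. One clause of the primary objective therefore has no data and no analysis behind it.

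What is at stake is the conclusion the trial may draw. The background argues that CHD pregnancies share a circulating angiogenic profile with preeclampsia and asks whether the maternal haemodynamic profile is also altered. That question compares CHD with non-CHD pregnancies. While the clause stands in the primary objective, a significant paired test or time trend within the cohort could be offered as an answer to it, although such a result carries no information on the comparison.

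**Working it through.** The protocol attaches no effect size, standard deviation or power to the 108, so there is no stated figure to reproduce. The check is whether the quantity can be identified at all.

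**1. What varies among eligible women**

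| Quantity | Place in the Protocol | Varies among eligible women? |
|---|---|---|
| Presence of a fetal cardiac anomaly | Aim; Primary Objective | No |
| Defect subtype | Secondary Objectives | Yes |
| Fetal cardiac function and morphology | Secondary Objectives | Yes |
| Maternal and perinatal outcome | Secondary Objectives | Yes |
| Time (gestation, postpartum) | Primary endpoint; mixed models; paired test | Yes, within each woman |

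Only the first row lacks variation. It cannot be read as meaning subtype, because subtype is a separate secondary objective.

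**2. Identifiability**

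Let X = 1 if the fetus has CHD and 0 otherwise, and let Y be any haemodynamic index.

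- The proportion of eligible women with X = 1 is p = 1, so Var(X) = p(1 − p) = 1 × 0 = 0.
- The slope of Y on X is Cov(X, Y)/Var(X) = 0/0, which is undefined. The correlation is undefined for the same reason.
- The design matrix with columns [1, X] has two identical columns, so its rank is 1 where 2 is needed. A numerical check with 108 rows of X = 1 gave variance 0, an undefined correlation and rank 1.

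None of these results depends on the number of women, so a larger sample would not help.

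**3. Whether the within-woman analyses can stand in**

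Write the mean change from baseline to the postpartum reading as a + b. Here a is the change that would be seen without CHD, and b is the extra change due to CHD. The cohort estimates only the sum. The protocol gives no value for a and no group from which to estimate it, so b cannot be separated, whatever a is. The same holds for the slope over gestation in the mixed models. The postpartum reading is taken in the same women within 72 hours of delivery, so it also reflects delivery and the early postpartum state. It is not an unaffected control.

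**4. Whether any comparator is mentioned elsewhere**

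The study design, population, variables and procedures, haemodynamic assessment, endpoints and statistical analysis mention no control group, historical cohort or normal-pregnancy reference values.

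**The case against.** **The clause is hedged and nothing rests on it.** This is fair. Both statements are tentative, the main verbs are to explore and to describe, and every planned analysis works within the CHD cohort. A reader might infer that the primary analysis is invalid or that the study fails. The documents do not support that: the primary endpoint and the planned tests can be estimated as they stand. Still, hedging does not supply a comparator, and the clause sits in the primary objective.

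**Some measured women may prove unaffected.** Readings begin at antenatal diagnosis, while eligibility needs postnatal confirmation, so some women may be measured and later found to have an unaffected infant. They would fail the inclusion criterion and are not a planned control group. The statement that CHD status is constant therefore applies to eligible women, not to everyone measured.

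**A separate SAP could name reference values.** It could, but it could not create variation in CHD status among enrolled women. The protocol's own analysis section mentions no outside comparator.

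**The primary endpoint is loosely worded.** Changes could mean change over time or alterations found in such pregnancies. The paired test and the mixed models favour the first reading. On the second, a comparator would again be needed.

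Two further inferences go beyond the documents. The first is that the changes to be observed are simply those of any normal pregnancy and delivery. The protocol describes no normal gestational or postpartum course, so this has no source in it, and the argument does not need it.

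The second is that 108 women set against an external reference would give a known precision. The arithmetic gives a 95% half-width of 1.96/√108 = 0.19 SD and a detectable shift at 80% power of (1.96 + 0.84)/√108 = 0.27 SD. These figures treat the reference as free of error and all 108 women as contributing. If the reference rested on 100 to 200 women (an assumption), the half-width would be 1.96 × √(1/108 + 1/100) = 0.27 SD to 1.96 × √(1/108 + 1/200) = 0.23 SD. The detectable shift would be about 0.39 to 0.33 SD. The documents identify no such reference, so none of these figures can be claimed.

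**Conclusion.** The concern holds for one clause. The association between maternal haemodynamics and the presence of fetal CHD cannot be estimated from eligible women at any sample size, because the exposure does not vary and no outside comparator is named. This rests only on the eligibility criteria and the absence of a comparator in the protocol, and it needs no numerical assumption.

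The descriptive clause of the primary objective stands. So do the secondary objectives on defect subtype, fetal cardiac function, outcomes and the number of preeclampsia cases, as far as this point goes. No planned test gives a wrong result because of the clause. What changes is the permitted conclusion: a change over gestation or after delivery may be reported as a description of this cohort, but not as a feature of CHD.

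**What to change.** Delete the clause on association with the presence of a cardiac anomaly from both the aim and the Primary Objective. Align the Primary Objective with the primary endpoint: maternal haemodynamics, and their change over gestation and to the immediate postpartum reading, within a cohort of CHD pregnancies. Add a sentence saying that no inference about CHD versus non-CHD pregnancies will be drawn. This needs no extra patients and no change to the planned analyses. Its cost is a more modest claim.

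Optionally, if the sponsor wants to keep the clause, specify before any analysis:

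- a named, gestation-specific normal-pregnancy reference obtained with the same device
- one primary index among the five haemodynamic indices listed
- an interval that includes the reference's own uncertainty
- a label marking the result as an external, non-randomised comparison

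No precision or power figure should be given until that reference is identified. This option costs additional analysis and depends on whether a suitable reference exists, which the documents do not show.

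### Plain correlations of absolute stroke volume, cardiac output and SVR carry maternal height by construction, because the device infers outflow-tract diameter from height; these between-woman analyses should adjust for maternal size

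*Protocol*

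**What the plan says.** - **Indices.** Variables and procedures lists "stroke volume (mL), cardiac output (CO) (L/min), systemic vascular resistance", together with heart rate and mean arterial pressure. No value indexed or standardised for body size is listed.
- **How the device obtains them.** Under Maternal hemodynamics assessment the protocol says "Using an internal anthropometric algorithm, which correlates the outflow tract diameter with the" patient's height, and then "USCOM-1A multiplies the velocity-time integral by the aortic root diameter to calculate stroke volume". CO is SV times heart rate. SVR is mean arterial pressure over CO. Both inherit the height-derived factor, SVR inversely.
- **Body size is recorded.** "Maternal height, weight and brachial blood pressure will be obtained prior to hemodynamic assessment". Pre-pregnancy weight is also on the variable list.
- **Analysis.** For defect type the Statistical analysis section specifies "calculating and testing Pearson's and/or Spearman's correlation coefficient, when necessary Kendall's correlation coefficient will be used", and the same approach for fetal cardiac function. Two of the secondary endpoints consist of calculating these coefficients. For outcomes it says "Regression analysis will be performed to explore the relationship between maternal hemodynamic parameters and maternal and perinatal outcome" and names no covariates. Only the mixed-model sentence undertakes to control for confounders, which it does not name. Baseline and postpartum values are compared by paired tests.

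**The concern.** Two women with identical blood velocity and heart rate, but different heights, receive different SV, CO and SVR. A bivariate coefficient cannot separate this from a haemodynamic difference.

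Where the other variable has nothing to do with maternal size, as one would expect for defect type, the result is only extra noise. Where it does vary with maternal size, the shared dependence on height produces an association with no haemodynamic content. Fetal cardiac dimensions may be such a variable. Estimated fetal weight and birthweight plausibly are, and they enter through the outcome regressions.

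The direction matters. Shorter women are assigned lower CO and higher SVR, and may have smaller babies. The protocol's background describes low CO with high SVR as the profile of early preeclampsia, so the artefact could be read as support for the hypothesis.

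**Working it through.** The only planning figure is N = 108. It comes with no effect size, SD or power, so there is nothing to reproduce; it is used here only as the number of women.

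**Inputs.** From the protocol: N = 108 and a significance level of 0.05 (taken as two-sided). Assumed, because the protocol gives no figures: diameter proportional to height; height 163 cm (SD 6.5), so its coefficient of variation (CV) is 6.5/163 = 4%; SV CV 20%; correlation of height with the other variable 0.2 to 0.3; no true association with blood velocity.

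**Height exponent.** Write SV = k × VTI × height^m, where VTI is the velocity-time integral. The protocol's literal wording (VTI times diameter) gives m = 1. A length times a length is an area, whereas a volume needs VTI times a cross-sectional area, which gives m = 2. The two are carried as a range.

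**Contrast between two women with the same VTI, 171 cm against 155 cm.**
- m = 1: 171/155 = 1.103, so SV and CO are 10% higher and SVR 9% lower (1/1.103 = 0.91).
- m = 2: 1.103² = 1.217, so SV and CO are 22% higher and SVR 18% lower (1/1.217 = 0.82).

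**Share of SV variance due to height.** Share = (m × CV of height / CV of SV)².
- m = 1: (0.04/0.20)² = 4%, so corr(SV, height) = 0.20.
- m = 2: (0.08/0.20)² = 16%, so corr(SV, height) = 0.40.

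**Induced correlation and false significance.** Induced r = corr(SV, height) × corr(height, other variable). At N = 108 a correlation is significant when |r| exceeds 0.189. By the Fisher transformation, the rejection rate is Φ(atanh(r)√105 − 1.96) + Φ(−atanh(r)√105 − 1.96).

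| m | corr(height, other) | induced r | false significance |
|---|---|---|---|
| 1 | 0.2 | 0.04 | 6.9% |
| 1 | 0.3 | 0.06 | 9.4% |
| 2 | 0.2 | 0.08 | 13.0% |
| 2 | 0.3 | 0.12 | 23.5% |

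A simulation of 20,000 studies per setting gave 9.1%, 13.0% and 23.8% for the last three rows. With height partialled out, all three fell to 4.9%.

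**Sensitivity.** With height CV 3.5-4.5%, SV CV 15-25% and height correlation 0.1-0.3, the range is 5-15% for m = 1 and 6-46% for m = 2.

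**Noise in defect-type comparisons.** Removing the height share shrinks the SD of SV by a factor √0.96 = 0.98 (m = 1) or √0.84 = 0.92 (m = 2), that is by 2% or 8%.

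**Paired comparison.** A woman's height factor is the same at both times. On the log scale it cancels exactly. On the raw scale, with m = 2, the simulated type I error was 4.6%.

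**The case against.** The strongest reply is that covariates are commonly left to a separate analysis plan, that body size is collected, and that the primary endpoint is a within-woman change. Much of this stands.

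- **Outcome regressions.** A reader might infer that these will be unadjusted, because only the mixed-model sentence mentions confounders. The protocol does not say so. It names no covariates and excludes none. The concern reaches the regressions only if they are in fact run without maternal size.
- **Primary endpoint.** A reader might infer that the haemodynamic changes themselves are biased. They are not. The paired comparison is unaffected, the mixed models promise confounder control, and heart rate and mean arterial pressure have no height-derived input.
- **Planned correlations.** These are with defect type and fetal cardiac parameters, not with birthweight. No reason appears why defect type should depend on maternal height, so noise is all that can be claimed there. For fetal cardiac parameters, false association is possible but not demonstrated.
- **Larger error rates.** Letting maternal weight contribute as well gives much higher figures: 18-46% if weight correlates 0.3 with SV and 0.2 with birthweight and is independent of height, and more if height and weight are correlated. Those figures rest on further assumptions. The protocol gives weight no role in the device's algorithm, so they do not measure the device artefact.

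The deferral argument does not remove the correlations. The protocol positively chooses bivariate coefficients, and makes them secondary endpoints, for indices it describes as derived from height. That is a stated method that fits the measurement poorly, not a detail left open.

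**Conclusion.** The point holds for the secondary between-woman analyses of SV, CO and SVR. The specified correlations contain a maternal-height component by construction: noise for defect type, and possible false association for anything that itself varies with maternal size.

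Under the central assumptions, false significance is about 7-9% if SV scales with height and 13-24% if it scales with height squared, against a nominal 5%. Adjustment restores about 5%. The CVs, the height correlations and the exponent are all assumptions, so these figures illustrate the size and do not predict it.

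The change is worth making because it is almost free, but the primary within-woman comparison does not depend on it.

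**What to change.** In the Statistical analysis section, for SV, CO and SVR only:

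1. With continuous fetal cardiac parameters, replace plain correlations by partial correlations, or regression, adjusted for maternal height and pre-pregnancy weight.
2. Compare defect types by a linear model or ANCOVA with the same two covariates. Defect type is nominal, so partial correlation does not suit it.
3. State that both covariates enter the outcome regressions, or height alone where events such as preeclampsia are few.
4. Keep absolute values for within-woman change.

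Under Maternal hemodynamics assessment, check the sentence that multiplies VTI by diameter against the device's actual calculation, since this determines how strongly height enters.

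The cost is one or two sentences in the analysis section and one or two degrees of freedom per model. No new data are needed.
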